5.1 Screening Procedures

Screening will be conducted in the prehospital setting by the initial EMS responder. Prehospital trauma life support interventions focusing on airway, breathing and circulation will be performed and an initial GCS score will be assessed by EMS to determine eligibility. The patient will be considered eligible if the initial GCS is ≤ 12 and the SBP has remained ≥ 90 mmHg prior to randomization, and other inclusion/exclusion criteria are met. If the GCS improves to greater than 12 prior to randomization, the patient will not be randomized. If the initial GCS is > 12 and during transport declines to ≤ 12 prior to administration of sedating and/or paralytic medication, the patient will become eligible if the SBP has remained ≥ 90 mmHg prior to randomization. If the SBP drops below 90 mmHg between randomization and administration of study drug or anytime thereafter, the patient will remain in the study and continue to receive the study drug.

5.2 Study Procedures

5.2.1 Randomization

Eligible patients will be randomly allocated in a proportion of 1:1:1 bolus/maintenance arm, bolus only arm, and placebo. Randomization assignments will be generated by the ROC DCC. To attempt balance by site, permuted blocks of varying concealed size will be used. Nevertheless, location of the episode and availability of providers determine which agency responds to the episode and the order in which the containers are used cannot be determined a priori. As a result, the randomization will represent a complete randomization rather than a permuted block randomization.

5.2.2 Prehospital intervention

Participating EMS vehicles will carry pre-randomized, sealed, numbered containers of study drug. After confirming the patient meets criteria for entry into the study, participating EMS providers will open the study drug kit on their vehicle. Patients are considered randomized if a study drug kit seal is broken in the presence of the patient based on the above screening criteria even if the drug is not administered. EMS providers will be instructed to obtain intravenous (IV) access prior to opening the study drug kit. Vascular access and fluid administration will be per standard protocol by the EMS agency. EMS will mix the drug and administer the bolus infusion as soon as life-saving interventions are performed. If IV medication in addition to TXA is required and only one IV access line is available, EMS will be instructed to clamp the IV tubing, flush the line with 10 ml saline, give the emergency drug IV push, flush the line again with 10 ml saline, and resume the TXA infusion. If the bolus infusion is stopped for reasons other than a protocol violation or a serious adverse event that may be associated with TXA, it is to be restarted and completed within 3 hours of the estimated time of injury either prior to ED arrival or after ED arrival and the in-hospital study drug infusion will be given. If it is anticipated that the bolus infusion cannot be completed within 3 hours of the estimated time of injury then it will not be resumed and the in-hospital study drug infusion will not be given.

After randomization, EMS will provide the kit ID# to research personnel upon arrival in the receiving ED. The research personnel will contact the study coordinating center and, using the kit ID#, obtain the unique code ID for the blinded study drug vial that matches the randomization assignment for the appropriate hospital infusion administration. In the rare case that the patient is brought to a non-participating facility, all study interventions will stop, the patient or patient's family member or legally authorized representative (LAR) will be informed that they were enrolled in the study and asked to give permission to obtain their medical information so they may be followed for primary and safety endpoints. In order to avoid this event, patients will only be eligible for this study if a determination is made that their destination is a participating hospital. This determination is made independent of the study and is based on standard local practices. Therefore, enrollment in the study will not delay transport to the participating hospital with the exception of any delay related to administering the drug.

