5.8 Early Termination of Study Drug

When EMS personnel open the blinded study drug kit, the patient is enrolled and randomized and will be included in the primary statistical analysis if the study drug is connected to the patient's IV access. The study drug will be terminated by EMS or by hospital providers for any of the reasons below.

- Prehospital provider suspects the patient has developed a thrombotic event (MI, ischemic stroke,) or seizure activity OR after hospital arrival the patient develops a thrombotic event (MI, PE, ischemic stroke, or symptomatic DVT) or seizure activity
- The patient requires cardiopulmonary resuscitation (CPR)
- The patient, patient's family member or legally authorized representative (LAR) withdraws from the study
- The patient is discovered to be pregnant
- A serum creatinine > 2.0 mg/dL is obtained
- The patient requires administration of Factor IX Complex concentrates or Anti-inhibitor Coagulant concentrates
- The patient is discharged from the hospital prior to completion of the 8 hour infusion

6. Study Outcome Measures

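### When the bolus can still be completed within 3 hours of injury, section 5.2.2 calls for restart and infusion after some events, chiefly CPR and need for coagulant concentrates, for which section 5.8 terminates study drug

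*Combined protocol and SAP*

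**What the plan says.** Section 5.2.2 (Prehospital intervention) opens its restart rule with "If the bolus infusion is stopped for reasons other than a protocol violation or a serious adverse event that may be associated with TXA". In that case "it is to be restarted and completed within 3 hours of the estimated time of injury", before or after ED arrival, and "the in-hospital study drug infusion will be given". The next sentence sets a limit: if completion within 3 hours of injury is not expected, "then it will not be resumed and the in-hospital study drug infusion will not be given".

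Section 5.8 (Early Termination of Study Drug) states: "The study drug will be terminated by EMS or by hospital providers for any of the reasons below". Because EMS is named, the rule covers the bolus as well as the hospital infusion. Seven reasons follow:
- a thrombotic event or seizure activity;
- CPR ("The patient requires cardiopulmonary resuscitation (CPR");
- withdrawal by the patient, family or representative ("legally authorized representative (LAR) withdraws from the study");
- pregnancy;
- renal function ("A serum creatinine > 2.0 mg/dL is obtained");
- need for Factor IX complex or anti-inhibitor coagulant concentrates;
- discharge before the 8-hour infusion ends.

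Section 5.2.3 (In-hospital intervention) has its own list of events that end study drug: completion, creatinine above 2.0 mg/dL, death, withdrawal, pregnancy or prisoner status, and a thrombotic event or seizure. CPR and coagulant concentrates are not on it.

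Sections 5.2.2 and 5.8 do not refer to each other.

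**The concern.** The restart rule is worded as an instruction, and its two exceptions are narrower than the termination list in 5.8. Where a 5.8 reason falls outside both exceptions and time remains, one section ends study drug while the other resumes the bolus and hangs the infusion.

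What is at stake is exposure in patients for whom 5.8 intends a stop. Under 1:1:1 allocation, two of the three arms receive TXA. Under 5.2.2 a patient in either active arm would go on to the full assigned regimen; under 5.8 the patient would have only what had run in by the stop. Staff at different sites could follow different sections in good faith, and neither choice would be a clear deviation.

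**Working it through.** This is a check of text against text. The plan states no figure that bears on it.

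**Step 1. Compare each 5.8 reason with the 5.2.2 exceptions and with the rest of the protocol.**

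| 5.8 reason | Within a 5.2.2 exception? | Settled elsewhere? | Result |
|---|---|---|---|
| Thrombotic event or seizure | Mostly, as an SAE possibly associated with TXA | Yes: 5.2.3, 8.6 and, for seizures, 5.2.7 stop drug whether or not the event is an SAE | No real conflict |
| CPR | Only if judged possibly associated with TXA | No: not on the 5.2.3 list | Conflict when judged not associated |
| Withdrawal | No | Yes: 5.2.3 ends drug; 9.3.1 and Appendix 1 make verbal withdrawal binding | Wording gap only |
| Pregnancy | Arguably, since it is an exclusion criterion (4.4) | Yes: 5.2.3 | Wording gap at most |
| Creatinine above 2.0 mg/dL | No | Yes: 5.2.3 and 5.2.7 | Wording gap; arises only if the bolus is running or restarted in hospital |
| Coagulant concentrates | No | No: not on the 5.2.3 list | Conflict |
| Discharge before the infusion ends | Not applicable | Concerns the infusion, not the bolus | No conflict |

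**Step 2. CPR in detail.** Section 8.6 counts a life-threatening occurrence as an SAE, so an event needing CPR would qualify. The 5.2.2 exception then depends on whether the event may be associated with TXA. If yes, 5.2.2 and 5.8 agree that the bolus is not restarted. If the arrest is put down to the injury alone, 5.2.2 calls for restart and 5.8 for termination. Section 5.8 makes no distinction by cause.

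**Step 3. Coagulant concentrates in detail.** Neither exception covers them. Section 5.2.3 leaves other hemostatic agents to the provider's discretion and asks that they be recorded, without saying that study drug ends. So 5.2.2 and 5.2.3 point to continuing and 5.8 to stopping.

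**Step 4. Can the events fall within the window?** Section 4.4 requires the bolus to start no later than 2 hours after injury, and 5.2.2 allows completion up to 3 hours. The latest permitted start therefore leaves 3 − 2 = 1 hour, and an earlier start leaves more. Section 5.2.3 lets an unfinished bolus run on after arrival, and 5.2.2 allows restart in the ED, so hospital events can overlap with the bolus.

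**Step 5. Difference in exposure.** Total TXA in a completed regimen is 1 + 1 = 2 g in the bolus/maintenance arm and 2 + 0 = 2 g in the bolus only arm. Under 5.8 it is the part of the bolus given before the stop.

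**Step 6. Effect on the analysis.** The primary population (8.1) and the safety population depend on treatment being started or connected, not completed. The choice of section can change membership only of subgroups 2 (full intervention) and 3 (prehospital intervention only) in 8.2, which the plan calls exploratory.

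**The case against.** The strongest reply is that the two sections have different subjects. The restart rule follows an instruction on pausing the line to give another drug, so it can be read as covering temporary interruptions, with 5.8 covering permanent stops. That reading is coherent and may be what was meant, but the text does not say so. The two exceptions in 5.2.2 are themselves reasons to end treatment, so the sentence reads as a complete list of stops that are not followed by restart. The brief pause for another drug is already dealt with in the preceding sentence.

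Other replies carry weight and narrow the point:
- The 3-hour limit removes the conflict whenever the bolus cannot be completed in time.
- A blinded provider may readily accept that an arrest could be associated with TXA, which brings CPR within the exception.
- The bolus runs wide open (5.2.7), so overlap with hospital events may be uncommon.
- Section 8.6 defers detail on early stopping to a manual of operations that is not among the documents. It may clarify the matter, but it should not have to settle opposite instructions within the protocol.

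A reader might infer that 5.2.2 orders drug to be resumed after a suspected seizure or thrombotic event that falls short of an SAE, or after withdrawal. The documents do not support this: the sections in the table stop drug in those cases.

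**Conclusion.** The text is wrong as written for two termination reasons: CPR not judged possibly associated with TXA, and need for Factor IX complex or anti-inhibitor coagulant concentrates. If either occurs during a bolus that could still be completed within 3 hours of injury, the protocol gives opposite instructions for the bolus and the infusion, and no other section resolves them. For creatinine and withdrawal, 5.2.2 is incomplete, but the rest of the protocol points to stopping.

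The number of patients affected cannot be estimated. The documents give no rate of bolus stops, and any count obtained by applying a percentage to the 963 patients would rest on that assumption alone.

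Two stronger readings should be avoided. A reader might infer that every stopped bolus must be restarted; the 3-hour limit rules that out. A reader might also infer a threat to the primary result; primary-analysis membership, power and alpha do not depend on this rule. The point matters for consistent handling of patients in whom 5.8 intends a stop, and it should be corrected on that ground.

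**What to change.** Reconcile sections 5.2.2, 5.2.3 and 5.8, and check them against 5.2.7 and the infusion discontinuation rules in 8.6. Use one list of termination reasons and refer to it from each section. State in 5.2.2 how the restart instruction relates to that list, so that each reason for stopping leads to one defined action for the bolus and one for the in-hospital infusion. The clinical team decides which action applies to each reason.

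Two further items belong in the same edit: prisoner status, which ends study drug in 5.2.3 but is not listed in 5.8, and arrival at a non-participating facility, which ends study treatment later in 5.2.2 but is not among the restart exceptions.

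The cost is a short amendment and matching changes to the EMS training material and manual of operations. No procedure, visit or analysis is added.

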5.2.3 In-hospital intervention

Research personnel will be responsible for obtaining the unique code identifier (ID) for the in-hospital blinded study drug vial that matches the prehospital study drug kit ID# randomization assignment by contacting the ROC Data Coordinating Center (DCC) by automated web based or phone system. The vial labeled with this unique code ID will be used to prepare the maintenance infusion appropriate for the randomization assignment of either 1 gm TXA 8 hour infusion or placebo 8 hour infusion. The maintenance infusion will be administered as soon as possible after arrival, and every effort will be made to begin administration within 3 hours of arrival or within 3 hours of completion of the prehospital infusion. If the infusion is not begun within 6 hours of hospital arrival or 6 hours from completion of the prehospital infusion, it will not be given. If the prehospital bolus infusion is not complete by the time the patient arrives to the hospital, it will be allowed to completely infuse and the maintenance infusion will be hung after completion of the bolus infusion. The subject will continue to receive the study drug as assigned until: (1) the study drug has completed the infusion, (2) the subject is demonstrated to have a serum creatinine >2.0 mg/dL at any time during study drug infusion, (3) the subject has died, (4) the patient, patient's family member or legally authorized representative (LAR) withdraws from the trial, (5) the subject is determined to be pregnant or a prisoner, or (6) the subject develops a thrombotic event (MI, PE, ischemic stroke, or symptomatic DVT) or seizure activity. If the patient is considered to be in hemorrhagic shock and the primary treatment team determines TXA should be administered as part of a massive transfusion protocol or based on local standard of care, emergency unblinding of the treatment arm will be immediately available to the hospital physician. All additional hemostatic agents and blood products will continue to be administered based on the discretion of the individual provider and according to local standard of care and will be recorded. Patients who develop hemorrhagic shock after randomization will continue to receive local standard of care treatment. If the treatment team is treating the patient for hemorrhagic shock and local standard of care includes administration of TXA, emergency unblinding will be required. The hospital physician will contact the ROC DCC's automated unblinding web base or phone system to obtain the field treatment arm if there is a need for rapid emergency unblinding. This will also automatically notify staff at the ROC DCC and the site research personnel via email of the emergency unblinding. The decision to administer additional TXA based on the patient's randomized treatment arm will be based on clinician judgment.

5.2.4 Treatment arms

There will be three treatment arms. The prehospital container for each treatment arm, also known as the study drug kit, will house the blinded study drug vial along with a label for a 250 mL bag of 0.9% sodium chloride for the bolus dose and labels for the IV tubing to flag the patient as enrolled in the TXA for TBI study. An EMS vehicle will carry the study drug kit as a part of their stock supplies. Each kit will be assigned and labeled with a randomization number, which EMS will communicate to the hospital-based research personnel, who then initiates the steps necessary to prepare the hospital infusion for administration.

5.2.5 Drug manufacture and supply

The active pharmaceutical ingredient (API) for the trial drug Tranexamic Acid Injection will be purchased from CUSTOPharm Inc. CUSTOPharm recently contracted with X Gen Pharmaceuticals Inc. for shared ownership of the API license. (see Appendix 4 for TXA Monograph) TXA Injection is a colorless solution packaged in a glass vial and manufactured by Exela Pharma Sciences, LLC in accordance with Good Manufacturing Practices (GMP). Exela will also manufacture the injectable placebo solution (sodium chloride 0.9%) in the same type of glass vial in accordance with GMP. The TXA and placebo vials, being identical in appearance, will be shipped separately in bulk to Almac Clinical Services. Almac will assemble the blinded study vials into custom study kits for the prehospital dose and in multiple mixed vial containers for the in-hospital dose, distribute them to the clinical sites and be responsible for maintaining the Product Specification File until final database lock and unblinding of the trial data.

5.2.6 Blinding

All providers will be blinded to the intervention assignment in a double blind manner. At no point will EMS or hospital providers be able to distinguish the treatment group unless emergency unblinding is required as described in section 5.2.3. Adherence to the treatment protocol will be carefully monitored and protocol deviations will be identified through the data collected or reported to the ROC DCC by study coordinators. The blinding process will involve labeling the prehospital study kits with randomization numbers that will be used as the package identification and labeling the in-hospital dose vials with unique code identifiers that can be matched to the study kit randomization numbers.

5.2.7 Justification for dose selection

The dose selection for the study drug is as follows:

- *Bolus/maintenance arm*: 1 gram IV TXA in 250 mL administered wide open followed by a 1 gram maintenance IV TXA infusion over 8 hours (weight based equivalent: 50 kg person – bolus 20 mg/kg, maintenance 2.5 mg/kg/h; 75 kg person – bolus 13.3 mg/kg, maintenance 1.7 mg/kg/h; 100 kg person – bolus 10 mg/kg, maintenance 1.25 mg/kg/h)
- *Bolus only arm*: 2 grams IV TXA in 250 mL administered wide open followed by a maintenance placebo infusion over 8 hours (weight based equivalent: 50 kg person – bolus 40 mg/kg; 75 kg person – 26.7 mg/kg bolus; 100 kg person – bolus 20 mg/kg)

The doses of TXA to be used in this study are based on studies of TXA in previous trauma trials including the CRASH-2 trial of TXA in trauma patients with significant hemorrhage as well studies performed in surgical patients. Loading doses in these studies have ranged from 2.5 mg/kg to 100 mg/kg with maintenance doses ranging from 0.25 mg/kg/h to 4mg/kg/h over 1-12h.⁴² Studies evaluating different dosing regimens of TXA on bleeding and transfusions have demonstrated no significant difference between the higher and lower doses. In cardiac surgical patients, a 10 mg/kg loading dose of TXA followed by an infusion of 1 mg/kg/h resulted in plasma concentrations sufficient to inhibit fibrinolysis, with no additional hemostatic benefit afforded by higher doses.^{77,78} In the CRASH-2 trial, there was no difference in the rate of vascular occlusive events (1.7% TXA versus 2.0% placebo) and no reported adverse events. In a study of patients with isolated TBI, a single 2 gram dose decreased ICH progression with no adverse events.

The dosing regimens in this proposal were chosen for the following reasons:

1. A fixed dose is most feasible in a prehospital study.
2. A single bolus dose without a maintenance infusion would be preferred for military application.
3. The adjusted per kilo doses for both interventional arms are in the range shown to inhibit fibrinolysis and provide a potential benefit in larger patients (>100 kg), yet have been shown to be safe without adverse effects in smaller patients (<50 kg).

Justification for using standard dosing in subjects with potential renal insufficiency: TXA is eliminated through renal excretion and thus, there is the potential risk of accumulation in patients with renal impairment; however,

the dosing regimen in both interventional arms of this trial involve either a low dose followed by a short course of TXA, or placebo, such that accumulation is expected to be minimal in either arm. For this study, if a history of renal dialysis is known by EMS prior to randomization, the patient will be excluded. If randomization has occurred and the patient's hospital serum creatinine is greater than 2 mg/dL at any time prior to or during the study drug infusion, the study drug infusion will be terminated.

Justification for use in subjects with potential hepatic impairment: Only a very small proportion of TXA is metabolized by the liver, thus there is no need for dose adjustment in hepatic impairment and pharmacodynamic interactions with other drugs should be minimal.

Justification for use in subjects with subclinical seizure activity not evident to EMS or care providers: In patients undergoing cardiac surgery, high doses of TXA have been associated with seizures;⁷⁹ however, in the CRASH-2 trial there were no reports of serious unexpected adverse events involving seizures in 20,211 trauma patients using similar doses proposed in this trial. In one retrospective review in patients who had undergone pulmonary endarterectomy with hypothermia, an increase in seizure activity compared to aprotinin was observed in patients without structural brain lesions (7 versus 0, $p=0.02$); however, the doses given were significantly higher than the doses to be administered in this trial.⁸⁰ For this study, observed seizure activity or a history of seizure activity will exclude the patient prior to randomization or, if randomization has occurred, cause administration of the study drug dose in the field or hospital to be stopped.

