All unanticipated problems involving risk to subjects or others, serious adverse events related to participation in the study and subject deaths related to participation in the study must be promptly reported by [contact]), by email ([contact]), or by [contact]) to the USAMRMC, Office of Research Protections, Human Research Protection Office. A complete written report will follow the initial notification. In addition to the methods above, the complete report will be sent to the U.S. Army Medical Research and Materiel Command, ATTN: MCMR-RP, [name]-us.

Infusion Discontinuation Rules: Any thromboembolic event (MI, PE, ischemic stroke, or symptomatic DVT) or seizure activity will prompt cessation of the infusion and a medical safety review. Further detail regarding specific clinical indications for stopping the study drug early will be provided in the manual of operations.

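### Sections 5.2.7 and 5.2.3 give different instructions when a seizure history is learned after randomization, and a smaller mismatch of the same kind affects creatinine

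*Combined protocol and SAP*

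**What the plan says.** The dose justification in Section 5.2.7 names two seizure triggers, observed activity and history. On history it says that "a history of seizure activity will exclude the patient prior to randomization or, if randomization has occurred, cause administration of the study drug dose". The end of that sentence gives the consequence after enrolment for both triggers: "if randomization has occurred, cause administration of the study drug dose in the field or hospital to be stopped". The same section deals with renal risk by ending the infusion if hospital creatinine is "greater than 2 mg/dL at any time prior to or during the study drug infusion".

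The in-hospital instructions in Section 5.2.3 say that the subject stays on assigned study drug until one of six events. The seizure event is "6) the subject develops a thrombotic event (MI, PE, ischemic stroke, or symptomatic DVT) or seizure activity". The renal event is "serum creatinine >2.0 mg/dL at any time during study drug infusion".

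Two other sections list reasons to stop:

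- Section 5.8 has seven bullets. The seizure bullet covers activity suspected by the prehospital provider, or the case where "after hospital arrival the patient develops a thrombotic event (MI, PE, ischemic stroke, or symptomatic DVT) or seizure activity". Its creatinine bullet uses the same 2.0 mg/dL threshold with no timing condition.
- The discontinuation rules in Section 8.6 state: "Any thromboembolic event (MI, PE, ischemic stroke, or symptomatic DVT) or seizure activity will prompt cessation of the infusion". They then refer to the manual of operations for further stopping indications.

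Exclusion 4 in Section 4.4 bars patients with a known seizure history, but only as far as EMS can establish it.

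**The concern.** Section 5.2.7 uses the history rule to justify the dosing with respect to seizures, in a trial run under exception from informed consent. Section 9.1 acknowledges an association between TXA and seizures, and seizures are a safety outcome. A safeguard stated for that purpose should also appear in the section that staff use to decide whether to hang or continue the infusion. In 5.2.3 it does not.

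Two things are at stake. The first is whether sites apply the stated safeguard in the same way. The second is whether a deviation can be classified at all. If a coordinator learns of a past seizure and the infusion goes ahead, that departs from 5.2.7 but complies with 5.2.3. If it is withheld, the reverse is true.

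**Working it through.** No figure in the plan is in question, so the check is a side-by-side reading.

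| Section | Seizure activity after randomization | Seizure history learned after randomization | Creatinine above 2.0 mg/dL |
|---|---|---|---|
| 5.2.7 | stops drug | stops drug | before or during the infusion |
| 5.2.3 (six items) | stops drug | in 0 of 6 items; drug continues until an item is met | during the infusion only |
| 5.8 (seven bullets) | stops drug | in 0 of 7 bullets; silent | no timing condition |
| 8.6 discontinuation rules | stops infusion | silent; more detail left to the manual | not mentioned |

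**Step 1: is there a conflict, or only an omission?** For 5.8 and 8.6 it is an omission. They give reasons to stop and say nothing about continuing. Section 5.2.3 is different, because it directs continuation until a listed event occurs and a past seizure is not one. Its grounds for not starting the in-hospital infusion concern timing, as do those in 5.2.2. Section 5.2.3 therefore conflicts with 5.2.7.

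**Step 2: can the case arise?** Yes.

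- Exclusion 4 depends on what EMS can find out about a patient with GCS of 12 or less.
- Section 5.4 says that the research coordinator cannot assess the patient at the scene.
- Section 9.3.1 places most contact with family or representatives after hospital arrival, and a history may surface then.

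**Step 3: how long is the window?** Section 5.2.3 lets the infusion start up to 6 hours after hospital arrival or after the bolus ends, and it runs for 8 hours. In-hospital exposure can therefore end as late as 6 + 8 = 14 hours after that reference point, if the infusion is not interrupted. Only a history learned before study drug ends meets the conflict.

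**Step 4: creatinine.** Suppose an emergency department value above 2.0 mg/dL returns after the bolus has finished and before the maintenance bag is hung. It meets the wording of 5.2.7 and, having no timing condition to fail, that of 5.8. It does not meet the wording of 5.2.3. Two of the three sections that give a creatinine rule already cover the case, so this is the lesser mismatch.

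**Step 5: what happens to the analysis?** Section 8.1 defines the primary population as everyone randomized who began treatment. Withholding or stopping the later infusion removes nobody. Membership of the Section 8.2 subgroups for full intervention and prehospital intervention only could shift with site practice, but the plan labels subgroup analyses exploratory.

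**The case against.** The best defence is that these sections are meant to be read together. Section 5.8 lists CPR, certain clotting-factor concentrates and hospital discharge, none of which is among the six items in 5.2.3. Section 5.2.3 lists prisoner status, which 5.8 omits. No single list is complete. Section 5.2.7 is also part of the Intervention chapter and is worded as an instruction. On that reading the history rule applies even though 5.2.3 leaves it out. The manual of operations may state it as well, and 5.2.2 contemplates stopping a bolus for a protocol violation.

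Part of this stands. The documents cannot show what staff would do at the bedside, because the manual is not available. The defence does not remove the conflict, though. A reader of 5.2.3 alone is told to continue, and nothing says that 5.2.7 takes precedence. Section 5.2.2 does not name seizure history, and a history that EMS could not have known may not count as a violation.

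A reader might infer more than the text supports in two ways:

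- That 5.8 and 8.6 also direct sites to start or continue the infusion. They do not; they are silent on history, and 8.6 is expressly open to further detail.
- That the protocol would have sites infuse patients with known epilepsy. A history known to EMS before randomization is an exclusion, so the case is limited to a history discovered later.

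**Conclusion.** The inconsistency is real. Sections 5.2.7 and 5.2.3 give different instructions for a seizure history learned after randomization and before study drug ends. Sections 5.8 and 8.6 do not settle the matter. The creatinine mismatch is real but smaller. Both conclusions rest on the protocol text alone, without the manual of operations.

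The number of patients affected cannot be derived. A reader might apply an assumed rate to the 963 patients; for example, 1% to 5% gives 963 × 0.01 to 963 × 0.05, or about 10 to 48. The documents give no such rate. A count of every history found after enrolment would also include those learned once study drug had ended, to which the conflict does not apply.

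A reader might also infer bias in the seizure comparison between arms. The documents do not show a route to it. Providers are blinded, so uneven handling has no stated way to differ by arm, and the primary analysis population is unchanged. What is at stake is consistent use of a stated safeguard and consistent classification of deviations.

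**What to change.** Reconcile Sections 5.2.3, 5.2.7, 5.8 and 8.6 so that all four state the same rule on two points: a seizure history learned after randomization, and a creatinine above 2.0 mg/dL obtained before the in-hospital infusion starts. Carry the same wording into the manual of operations. Which rule applies on each point is for the sponsor and the medical monitor to decide.

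It would also help to record the date and time at which the history or result became known, so that handling can be audited.

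The cost is a wording amendment and, if the timing is recorded, one field on an existing form. No extra patients or procedures are needed.
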